5.2. Ingenio 2 CRT-P Indications for Use

The Ingenio 2 CRT-Ps are indicated for patients who have symptomatic congestive heart failure (CHF) including LV dysfunction and wide QRS, and/or one or more of the following conditions:

- symptomatic paroxysmal or permanent second- or third-degree atrioventricular (AV) block
- symptomatic bilateral bundle branch block
- symptomatic paroxysmal or transient sinus node dysfunction with or without associated AV conduction disorders (i.e., sinus bradycardia, sinus arrest, sinoatrial [SA] block)
- bradycardia-tachycardia syndrome, to prevent symptomatic bradycardia or some forms of symptomatic tachyarrhythmias
- neurovascular (vaso-vagal) syndromes or hypersensitive carotid sinus syndromes.

Atrial tracking modes are also indicated for patients who may benefit from maintenance of AV synchrony. Dual-chamber modes are specifically indicated for treatment of the following:

- conduction disorders that require restoration of AV synchrony, including varying degrees of AV block
- VVI (ventricular single chamber mode) intolerance (i.e., pacemaker syndrome) in the presence of persistent sinus rhythm
- low cardiac output or CHF secondary to bradycardia.

Adaptive-rate pacing is indicated for patients exhibiting chronotropic incompetence and who would benefit from increased pacing rates concurrent with increases in MV and/or physical activity.

Please refer to the Instructions for Use (IFU) for the most complete labeling instructions.

5.3. Ingenio 2 CRT-P Contraindications

BSC Ingenio 2 CRT-P devices have the following contraindications:

- in patients who have a separate ICD with transvenous leads
- unipolar pacing or use of the MV/Respiratory Sensor with a subcutaneous ICD (S-ICD) is contraindicated because it may cause inappropriate therapy or inhibition of appropriate S-ICD therapy.
- MV is contraindicated in patients with both unipolar atrial and ventricular leads
- single-chamber atrial pacing is contraindicated in patients with impaired AV nodal conduction
- atrial tracking modes are contraindicated in patients with chronic refractory atrial tachyarrhythmias (atrial fibrillation or flutter), which might trigger ventricular pacing.
- asynchronous pacing is contraindicated in the presence (or likelihood) of competition between paced and intrinsic rhythms.

Please refer to the IFU for the most complete labeling instructions.

6. Study Objective

The objective of this post market clinical follow-up (PMCF) is to collect data on the performance of the Ingenio 2 CRT-P devices and to document that device-related events, device malfunctions or DDs do not increase safety risks in Ingenio 2 CRT-Ps, both in general and specific to the new features and hardware of the devices.

7. Endpoints

7.1. Primary Safety Endpoint

The primary safety endpoint of this study is to:

- evaluate and document the device-related complications by assessing the device-related complication free rate (DRCFR) at the 3 months post-implant.

Device-related complication is defined as complication (an AE that resulted in death, serious injury, a correction using invasive intervention, or permanent loss of device functions) assessed as related to the device.

7.2. Primary Effectiveness Endpoint

The primary effectiveness endpoint for this study is:

- LV pacing threshold measurements performed at 0.5 ms pulse width at 3 months post-implant

The pacing configuration selected for permanent programming will be compared to prospectively determined limits.

7.3. Secondary Safety Objectives

The secondary safety objectives for this study are:

- Assessment of proper function of the PaceSafe-LVAT feature with special attention to:
 - inappropriate loss of capture due to LVAT (not related to lead dislodgement, connection issue, etc.) and
 - devices which show retry into LVAT followed by Latitude alert
- Assessment of reported events in relation to the use of MICS during all visits
- Assessment of all reported events in relation to the Quad Lead and Header.

7.4. Secondary Effectiveness Objectives

The secondary effectiveness objectives for this study include:

- Collection of user experience with the PRM interface through the Product Experience Reporting at implant and during follow-up
- Assessment of LV pacing at implant and follow up (pacing threshold per vector, Impedance per vector, % pacing)
- Assessment of battery voltage at Latitude based Close-out visit, for all devices. A battery voltage of $\leq 75\%$ of expected power level (based on the theoretical power consumption calculation in respect to the programmed parameters) will be investigated further.
- Assessment of POST: number of out of range impedance alerts not related to mitigating factor (header connection issue, lead failure, lead dislodgement, etc.)
- Assessment of the correlation between 6 minute walking test distance at 1 month and 3 months post-implant and for subjects with an HRS < 50 and ≥ 50
- The HRS changes between 1 month follow-up and 3 month follow-up will be analyzed for all subjects, for subjects with HRS < 50 and ≥ 50 , and for subjects in a non-rate adaptive mode and with rate adaptive pacing.

All event data may be combined with data from Ingenio 2 devices enrolled into the Gentle study.

8. Design

This study is prospective, non-randomized, multi-center, single-group PMCF study.

8.1. Scale and Duration

Sixty-two eligible subjects planned for implant with an Ingenio 2 CRT-P will be enrolled in this study from 10-15 investigational centers, including but not limited to: Belgium, Denmark, Finland, Germany, Netherlands, and Spain. If a site does not enroll a subject within a 3-month time period, the site may be replaced by the discretion of the sponsor.

Enrollment is expected to take approximately 12 months. Subjects will be followed for 3 to 16 months after implant with a median follow-up time of 1 year. All study required visits will be completed as part of a regularly scheduled clinic visit.

The study will be considered complete (primary endpoint completion) after all subjects have completed the Latitude based Close-out 3 to 4 months (91 – 120 days) after last study enrollment. The analysis is planned for 2016. Study completion is anticipated in 2016.

8.2. Treatment Assignment

This study is a non-randomized non-blinded post-market study intended to evaluate the Ingenio 2 CRT-P (VISIONIST) device in a clinical setting. All enrolled subjects will receive an Ingenio 2 CRT-P and the treatment assignment will be based on an “all-comers” consecutive basis. The study devices are fully commercially available and all subjects are planned to receive a CRT-P implant. The assignment of the specific Ingenio 2 device will be determined by the physician; all leads currently in place from previously implanted devices and planned new leads (e.g., Acuity X4 and/or other LV leads) are to be allowed.

8.3. Justification for the Study Design

The primary objective of this study is to gather data to establish the chronic safety, performance and effectiveness of Ingenio 2 CRT-P and to obtain “standard” clinical data on the device use in the clinical setting. In order to obtain a “real world” picture of the CRT-P, the study Inclusion/Exclusion Criteria and follow-up schedule has been written generally enough to allow for study center specific standard of practice that should accurately capture the device use in a “standard” clinical setting. Additionally, by requiring study centers to follow their specific standard of practice, risk to the subject is minimized because the treatment received by the subject will be similar to the treatment the subject would receive if not participating in the study. For this same reason, device implantation is not randomized as it will be determined by the study doctor, based on implanted leads already in place and other medical factors.

Determination of sample size is provided in Section 12.3.

9. Subject Selection

9.1. Study Population and Eligibility

Inclusion and Exclusion criteria are listed in Sections 9.2 and 9.3 below.

Subjects who are enrolled but later determined to not fulfill all inclusion and exclusion criteria after an attempted 3-lead device system implant will be considered to have incurred a Clinical Investigation Plan (CIP) deviation. These subjects will not be included in the planned data analysis but will be followed until the end of the study. Subjects who were intended to be implanted with a Visionist device, or who did not receive a Visionist device after an attempted implant should be withdrawn 30 days after the unsuccessful attempt if all pending events are closed. Once it has been

determined that a subject did not fulfill any inclusion/exclusion criteria, only observational data will be collected for that subject at any visit attended.

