Statistical Test Method	
Sample Size Methodology:
 
 • Sample size for the primary safety endpoint was calculated using exact binomial methods for comparison of a single proportion to a performance goal. • Sample size for the primary effectiveness endpoint was calculated using one-sample t-test methodology for comparison of a single mean to a performance goal. 
Analysis Methods:
 
 • The DRCFR from implant will be calculated as the proportion of actively enrolled subjects without a device-related complication through 3 months after implant. The null hypothesis will be rejected and the endpoint considered met if the lower one-sided 95% confidence bound for the proportion of subjects with no device-related complication is greater than 87.5%. • Regarding mean LV pacing threshold at 3 months post-implant, the null hypothesis will be rejected and this endpoint considered met if the upper one-sided 95% confidence bound for the mean LV pacing threshold at 3-months is less than 2.5V. 
Further details on analytical methods can be found in Section 12.0 of the CIP.

Sample Size Parameters	
DRCFR through 3 months post-implant: 62 subjects. Sample size was calculated assuming a 97.5% DRCFR, a performance goal of 87.5%, one-sided alpha level of 0.05, 80% power, and 20% attrition.
 
Mean LV pacing threshold at 3 months post-implant: 45 subjects. Sample size was calculated assuming a mean (\pm standard deviation [SD]) LV pacing threshold of $1.9 \pm 1.2V$, a performance goal of 2.5V, one-sided alpha level of 0.05, 90% power, and 20% attrition.
 
Based on the above sample size calculations, the minimum required sample size to statistically power the primary endpoints is 62 subjects.

3. Table of Contents

1. TITLE PAGE	1
2. CLINICAL INVESTIGATION PLAN SYNOPSIS	4
3. TABLE OF CONTENTS.....	10
3.1. Table of Figures.....	13
3.2. Table of Tables	14
4. INTRODUCTION	15
5. DEVICE DESCRIPTION.....	18
5.1. Ingenio 2 Cardiac Resynchronization Therapy Pacemakers.....	18
5.1.1. PaceSafe.....	21
5.1.2. Post-Operative System Test.....	21
5.1.3. Atrial Arrhythmia Reports	22
5.1.4. ECG/EGM Snapshots	22
5.1.5. Leads.....	22
5.1.6. ZIP Telemetry	22
5.1.7. Programming System.....	22
5.2. Ingenio 2 CRT-P Indications for Use	23
5.3. Ingenio 2 CRT-P Contraindications.....	24
6. STUDY OBJECTIVE	24
7. ENDPOINTS	24
7.1. Primary Safety Endpoint.....	24
7.2. Primary Effectiveness Endpoint	24

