10.3. Subject Status and Classification

Consent ineligible subject

A study subject who has signed informed consent but is found to not meet eligibility criteria will be considered a consent ineligible subject and will not count towards the enrollment ceiling. There are no follow-up or AE reporting requirements for consent ineligible subjects. The original signed Informed Consent must be maintained in the center's administrative file.

Active enrolled subject

A study subject who meets the eligibility criteria as per Section 9.2 and Section 9.3 and has signed and dated the Subject ICF is considered actively enrolled in the study. These subjects are followed in accordance with the CIP follow-up schedule and included in the foreseen study analysis. The original signed Subject ICF and any applicable documentation must be maintained in the center's subject file. All applicable eCRFs per the CIP must be completed.

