12.1.1.2. Statistical Methods

When the final study subject reaches the 3 Month required follow-up visit, the primary safety analysis will be performed based on exact binomial methods for the estimation of the DRCFR, including the exact lower one-sided 95% confidence bound. Subjects that die/withdraw or are lost-to-follow-up prior to the 3-month endpoint evaluation ($\leq 91 + 21$ days post-implant or post-implant attempt) and have not experienced device-related complications will be excluded from the analysis. The sample size was adjusted to account for up to 20% attrition to ensure there would be a sufficient number of evaluable subjects through 3-months.

The primary safety endpoint will evaluate the DRCFR through 3-months post-implant (or implant attempt), calculated using exact binomial methods. The null hypothesis will be rejected and the endpoint considered met if the lower one-sided 95% confidence bound for the DRCFR at 3-months is greater than 87.5%.

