12.4. General Statistical Methods

12.4.1. Analysis Sets

All subjects where implant with the Ingenio 2 CRT-P device was successful will be included in the primary endpoints analyses. For the DRCFR primary endpoint, subjects where the Ingenio 2 CRT-P device was attempted but not successfully implanted will also be included. Nevertheless, for the DRCFR primary endpoint, subjects that die/withdraw or are lost-to-follow-up prior to the 3-month endpoint evaluation (91 days post-implant or post-implant attempt) and have not experienced device-related complication will be excluded from the analysis.

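### Sections 9.1 and 12.4.1 define the primary safety set differently for implanted subjects later found ineligible, and no passage says which governs

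*Combined protocol and SAP*

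**What the plan says.** Section 9.1 covers subjects who were enrolled, had an attempted 3-lead implant and were then found not to meet the criteria: "These subjects will not be included in the planned data analysis but will be followed until the end of the study". Subjects who did not receive the device are dealt with separately in the same section; they "should be withdrawn 30 days after the unsuccessful attempt if all pending events are closed". Section 10.1 likewise gives subjects who do not receive the implant 30 days of safety follow-up and then withdraws them.

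Section 12.4.1 sorts by implant outcome only: "All subjects where implant with the Ingenio 2 CRT-P device was successful will be included in the primary endpoints analyses". For the DRCFR, "subjects where the Ingenio 2 CRT-P device was attempted but not successfully implanted will also be included". Its one exclusion is death, withdrawal or loss before 91 days without a device-related complication. Section 12.1.1.2 has an exclusion of the same kind, for subjects who leave early and "have not experienced device-related complications will be excluded from the analysis", but its limit is 91+21 days.

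The synopsis (Statistical Test Method) takes as the DRCFR "the proportion of actively enrolled subjects without a device-related complication" and adds: "Further details on analytical methods can be found in Section 12.0 of the CIP". Section 10.3 defines the active enrolled subject as one who meets Sections 9.2 and 9.3 and has signed consent, and says such subjects are "included in the foreseen study analysis".

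**The concern.** The ineligible group in Section 9.1 must include implanted subjects, because it is followed to study end while failed attempts leave at about 30 days. Such a subject is out of the DRCFR under 9.1 and in under 12.4.1. Two analysts, each following current text, could reach different verdicts on the primary safety endpoint from the same data. The study is unblinded (Section 8.2) and events are reviewed at least monthly (Section 21.1), so an unsettled rule could be settled with the result in view.

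Two related gaps affect the same denominator. The two attrition cut-offs disagree: an event-free withdrawal on day 100 is excluded by 12.1.1.2 and kept by 12.4.1. And because attempts are withdrawn at about 30 days, an event-free attempt drops out under either cut-off while an attempt with a complication counts, although 12.4.1 says attempts are included. Whether an attempt enters the denominator then depends on its outcome.

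**Working it through.** **1. The plan's own figure.** Inputs from Section 12.3 and Table 12-1: goal 87.5%, expected DRCFR 97.5%, one-sided alpha 0.05, power 80%, attrition 20%. For f complications in n subjects, the exact one-sided 95% lower bound is the 5th percentile of Beta(n−f, f+1); the endpoint is met if it exceeds 0.875.

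- Most complications that still pass: 1 at n=48, 2 at n=49–59, 3 at n=60–62.
- n=49: P(X≤2) is 0.0461 at a 12.5% complication rate (alpha) and 0.876 at 2.5% (power). At n=48 power is 0.662. So 49 is the smallest n with at least 80% power.
- 49/0.8 = 61.25, so 62 to enrol.

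Both stated figures reproduce.

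**2. Can one subject change the verdict?** The counts are illustrations.

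| Later-ineligible subject | Under 12.4.1 | Under 9.1 |
|---|---|---|
| Had a complication | 4/62, bound 85.84%, fail | 3/61, bound 87.78%, pass |
| Event-free | 2/49, bound 87.70%, pass | 2/48, bound 87.46%, fail |

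**3. How often?** Assume DRCFR 97.5% and ineligibility unrelated to outcome. The documents give no number of ineligible subjects, so take k = 1 to 3. Let n be the set under 12.4.1 and n−k the set under 9.1, and sum the exact binomial probabilities of outcomes where the verdicts differ.

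For k=1:

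- n=49: exactly 2 complications among the other 48, and the ineligible subject event-free. 1128 × 0.025² × 0.975⁴⁶ × 0.975 = 21.4%, all pass-to-fail.
- n=60: exactly 3 among the other 59, and the ineligible subject event-free: 12.0%, all pass-to-fail.
- n=50–59: exactly 2 among the others, and the ineligible subject has the complication: 0.56–0.63%, fail-to-pass.
- n=61–62: exactly 3 among the others, likewise: 0.32%, fail-to-pass.

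| n | k=1 | k=2 | k=3 |
|---|---|---|---|
| 49 | 21.4% | 20.6% | 19.7% |
| 55 | 0.6% | 1.2% | 1.8% |
| 60 | 12.0% | 11.4% | 10.8% |
| 62 | 0.3% | 0.6% | 11.5% |

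The large values arise where removal crosses a step in the allowed count (49 to 48, 60 to 59). With k=2 the step is also crossed from n=50 and n=61; with k=3, from n=50, 51, 61 and 62. Fail-to-pass stays below 2% for k = 1 to 3 at every n from 49 to 62.

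**4. Attempts.** Take 58 implanted subjects with 2 complications, plus 2 attempts, one with a complication (assumed counts). Both attempts counted: 3/60, bound 87.58%, pass. Event-free attempt dropped by the attrition rule: 3/59, bound 87.38%, fail. No attempts: 2/58, bound 89.5%, pass.

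**The case against.** The best defence is that Section 9.1 acts as a prior filter: Sections 10.1 and 11.2 make eligibility a condition of enrolment, Section 10.3 places eligible subjects in the analysis, and 12.4.1 then sorts them by implant outcome. That reading is possible. But 12.4.1 speaks of all successful implants, lists its own exclusion and does not refer to 9.1, and 12.1.1.2 has no eligibility condition either. The text does not settle it. Section 12.5.4 requires changes before the primary analyses to go into an approved, amended SAP; that limits a late choice, but choosing between two existing rules may not count as a change.

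Several objections stand and limit the point:

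- A reader might infer that the synopsis expressly excludes ineligible subjects. It appears to agree with 9.1, but only by inference through Section 10.3. Section 9.1 itself calls these subjects enrolled, and they do not fit the consent-ineligible class, which has no follow-up. The direct clash is 9.1 against 12.4.1.
- A reader might take 21.4% as the usual risk. It belongs to one set size, reached only after nearly the full 20% attrition. With one ineligible subject the usual value is below 1%.
- A reader might infer a bias towards passing, for instance through exclusion 7, a discretionary judgement made during the implant. The wording leaves open that a subject is removed after an intra-procedural complication, but nothing shows that it would happen.
- Which set should be primary is partly a choice. Naming either in advance would remove the conflict.

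**Conclusion.** The conflict is real and should be resolved before the primary analysis. An implanted subject later found ineligible is excluded by 9.1 and included by 12.4.1, with no rule of precedence, and one such subject can reverse the primary safety verdict in either direction. Assuming the planned 97.5% DRCFR, one ineligible subject and ineligibility unrelated to outcome, disagreement has probability about 0.3–0.6% at most n from 50 to 62, rising to 21.4% at n=49 and 12.0% at n=60. Those two values are passes turned into fails under 9.1; the reverse stays below 2% for one to three ineligible subjects. If ineligibility is related to outcome, these probabilities do not apply.

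The two attrition cut-offs and the outcome-dependent treatment of attempts are confirmed from the text. None of this makes the sample size wrong: 49 for analysis and 62 to enrol are correct.

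**What to change.** Before the primary analysis, align the synopsis and Sections 9.1, 10.3, 12.1.1.2 and 12.4.1:

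- Define the DRCFR set as all subjects with a Visionist implant or attempted implant, regardless of eligibility findings made during or after the procedure. State that the 9.1 exclusion does not apply to the primary safety endpoint.
- Report the eligible-only DRCFR as a sensitivity analysis.
- Use one attrition cut-off in 12.1.1.2 and 12.4.1.
- Apply one rule to attempts that does not depend on outcome, and report the DRCFR with and without them. Do not simply assume that an attempt event-free at 30 days is complication-free at 3 months, since that credits time not observed.
- State which set applies to the LV pacing threshold. Section 12.1.2.2 takes implanted subjects with an available threshold and also has no eligibility condition.

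The cost is wording in five places, with no extra subjects or visits. The reported DRCFR may shift slightly in either direction. Three-month data may be less complete in ineligible subjects, because 9.1 limits them to observational data at visits they attend.

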9.2. Inclusion Criteria

Subjects who meet all of the following criteria (Table 9-1) may be given consideration for inclusion in this clinical investigation, provided no exclusion criterion (Table 9-2) is met.

Table 9-1: Inclusion Criteria

1. 18 years or above, or above legal age to give informed consent specific to state and national law
2. Willing and capable of providing informed consent
3. Planned to be implanted or replaced with a VISIONIST Ingenio 2 CRT-P device
4. Planned to be implanted with a 3-lead CRT-P system
5. Planned to be connected to the remote data collection through the Latitude® system
6. Able to do a 6 minute walk test
7. Maximum sensor rate of APMHR 80% should be clinically acceptable
8. Willing and capable of participating in all visits associated with this study at an approved clinical study center and at the intervals defined by this CIP.

9.3. Exclusion Criteria

Subjects who meet any one of the following criteria (Table 9-2) will be excluded from this clinical study.

Table 9-2: Exclusion Criteria

 1. Documented life expectancy of less than 12 months 2. Currently on the active heart transplant list 3. Enrolled in any other concurrent study without prior written approval from BSC, with the exception of local mandatory governmental registries and observational studies/registries that are not in conflict and do not affect the following: 
 o Schedule of procedures for the Rally CRT-P Study (i.e., should not cause additional or missed visits) o Rally CRT-P Study outcomes (i.e., involve medications that could affect the heart rate of the subject) o Conduct of the Rally CRT-P Study per Good Clinical Practice (GCP)/ International Standard Organization (ISO) 14155:2011/ local regulations as applicable 4. In chronic atrial fibrillation 5. Age predicted maximal heart rate (APMHR) needs to be programmed < 80% for clinical reasons at time of enrollment. 6. Not planned to receive a functional atrial lead 7. Per the implanting physician's discretion, subject is not a suitable candidate to receive the study device as determined during the implant procedure 8. Women of childbearing potential who are or might be pregnant at the time of study enrollment 9. Unwilling or unable to participate in all scheduled study follow up visits at an approved study center 10. Does not anticipate being a resident of the area for the scheduled duration of the trial.

10. Subject Accountability

